### 9.2. Study Design Considerations

#### 9.2.1. Sample Size Assumptions

It is planned that a total of 140 subjects will be randomised in a 1:1 ratio i.e. 70 subjects in each treatment arm. LAP117314 is an exploratory Phase II study, and the sample size is not based on the number of subjects required to achieve a statistically significant pre-specified reduction in the control incidence of diarrhoea.

The overall incidence of diarrhoea associated with treatment with lapatinib and capecitabine ranges from less than 40% to more than 80% across a number of studies (Section 1.1). Only limited data are available on the incidence of diarrhoea with a severity of Grade 2 or more which can be used as a basis for sample size estimation. It is likely that the implementation of active diarrhoea management guidelines will limit the incidence of more severe diarrhoea which develops as a progression from inadequately treated mild diarrhoea. Therefore, a conservative approach has been taken in LAP117314, and data from study EGF111438, which shows the lowest incidence of diarrhoea with a severity of Grade 2 or more (20%), has been used as the basis for the power calculations. In addition, power calculations have been conducted based on a less conservative approach using data from EGF100151, in which diarrhoea management guidelines were not implemented and in which the incidence of diarrhoea with a severity of Grade 2 or more was 32%.

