#### 9.2.2. Sample Size Sensitivity

Based on the results of EGF111438, an incidence of 20% of Grade 2 or higher diarrhoea is assumed for subjects who receive lapatinib and capecitabine with no prophylactic octreotide. The power for the analysis to detect a reduction in the incidence of Grade 2 or higher diarrhoea from 14% to 8% ranges from 69% to 25%, if the assumed incidence in the control arm is 20%, using a one-sided test with an alpha level of 0.025 (Table 21).

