##### **9.3.4.2. Futility Analysis of Primary Endpoint**

A futility analysis of the incidence of Grade 2 diarrhoea, the primary endpoint, comparing this incidence between the group of subjects who receive lapatinib and capecitabine to the group of subjects who receive no prophylactic octreotide will be performed. This will take place at a single interim analysis after approximately 40% of subjects (60 subjects) have had at least 9 weeks of study treatment.

Early termination of the study will be considered by the independent review committee. Their recommendation will be based on the following points:-

- Whether it would be possible to draw any meaningful conclusions if the study were to continue to planned completion given the:-

- The clinical relevance of the observed incidence of Grade 2 diarrhoea.
- The conditional power based on data from approximately 40% of the patients
- The totality of the evidence observed.

For example:

- If the diarrhoea rate is 30% in the control arm, in order for the conditional power (under the current trend) to be around 50% to see a positive result at the end of the trial, we would need to see a diarrhoea rate of 16% or lower in the octreotide arm. (Equating to a difference in 14% in incidence between treatment arms)
- If the diarrhoea rate is 20% in the control arm, in order for the conditional power (under the current trend) to be around 70% to see a positive result at the end of the trial, we would need to see a diarrhoea rate of 6% or lower in the octreotide arm. (Equating to a difference of 14% in incidence between treatment arms)

The conditional power will need to be re-calculated based on the actual incidence and actual percentage of patients evaluated at the time of the interim analyses.

It is envisaged that if at least a modest improvement in the diarrhoea rate in the octreotide arm is not seen with a conditional power of at least 50% at the interim analysis, it is unlikely that the trial would justify octreotide use in clinical practice. Further confidence intervals around the estimate of the observed difference in incidence of Grade 3 diarrhoea will be provided to aid clinical judgement.

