### **9.3.5. Key Elements of Analysis Plan**

The final analysis will take place when all subjects have completed the study.

Data will be listed and summarised according to the GSK reporting standards, where applicable. Complete details will be documented in the Reporting and Analysis Plan (RAP). Any deviations from, or additions to, the original analysis plan described in this protocol will be documented in the RAP and final study report.

As it is anticipated that accrual will be spread thinly across centers and summaries of data by center would be unlikely to be informative, data from all participating centers will be pooled prior to analysis.

All data up to the time of study completion (24 weeks or early withdrawal from the study) will be included in the summaries, regardless of the duration of treatment.

As the duration of treatment for a given subject will depend on efficacy and tolerability, the duration of treatment will vary between subjects. Non-responder imputation will be used in the case of missing data for the analysis of the primary endpoint based on the ITT population. Subjects who withdraw from the study prior to the Week 9 visit without experiencing Grade 2 diarrhoea or above will be assumed to have experienced Grade 2 diarrhoea or above for the purpose of the analysis. Similar imputation techniques will be

used for the m-ITT population analysis of the primary endpoint. No imputation will be performed for the Per Protocol analyses. Imputation methods for the secondary endpoints will be considered and detailed as appropriate in the RAP.

Demographic and screening characteristics will be summarised.

Details on the determination of tumour response are given in Section 7.1.11. There will be no adjustments for multiplicity.

Details on efficacy summaries are provided in Section 9.3.5.1 and details on safety summaries are provided in Section 9.3.5.2.

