2.5.2 Statistical hypothesis, model, and method of analysis

2.5.2.1 Diarrhoea of Grade 2 and above during the first 3 cycles treatment

This study is designed to test the superiority of prophylactic octreotide vs. no prophylactic octreotide in reducing the proportion of subjects experiencing diarrhoea with a severity of 2 or higher during the first 9 weeks (i.e., 3 cycles treatment) of lapatinib and capecitabine. Superiority will be assessed using data from the Intent-to-Treat population. The following statistical hypothesis will be tested to address the primary efficacy objective:

$$H_0: \delta = 0 \text{ vs. } H_a: \delta < 0,$$

where δ is the difference in the incidence of Grade 2 or higher diarrhoea between prophylactic vs. no prophylactic octreotide during the first 3 cycles of lapatinib and capecitabine.

The AE term ‘diarrhoea’ will be used to select episodes of diarrhoea.

Episodes of diarrhoea ‘during the first 3 cycles of treatment’ are defined as those with an onset date on or after the efficacy reference start date as defined in [Section 2.1.3.2](#) and before the Cycle 4 visit date.

Subjects who withdraw from the study on or prior to the Cycle 4 visit date will be assumed to have experienced diarrhoea (non-responder imputation) of grade 2 or higher.

The superiority of prophylactic octreotide compared to no prophylactic octreotide will be assessed using a Pearson chi-square test in ITT population. The implementation of the Pearson chi-square test is specified in [Section 5.3.1](#). The proportion of subjects experiencing at least one episode of diarrhoea with a severity of Grade 2 or higher in each treatment group, the difference in proportions between the treatment groups, the corresponding 95% confidence interval and the two-sided p-value from the chi-square test will be presented.

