3.2 Sample Size Sensitivity

Based on the results of EGF111438, an incidence of 20% of Grade 2 or higher diarrhoea is assumed for subjects who receive lapatinib and capecitabine with no prophylactic octreotide. The power for the analysis to detect a reduction in the incidence of Grade 2 or higher diarrhoea from 14% to 8% ranges from 69% to 25%, if the assumed incidence in the control group is 20%, using a one-sided test with an alpha level of 0.025 ([Table 3-1](#)).

Table 3-1 Sensitivity of sample size based on 20% control incidence of Grade 2 or more diarrhoea

Incidence, no prophylactic octreotide	20%	20%	20%	20%	20%
Incidence, prophylactic octreotide	6%	7%	8%	10%	12%
Estimated Statistical Power	69%	61%	53%	37%	25%
Subjects per Treatment group	70	70	70	70	70

Based on the results of EGF100151, an incidence of 32% of Grade 2 or higher diarrhoea is assumed for subjects who receive lapatinib and capecitabine with no prophylactic octreotide. The power for the analysis to detect a reduction in the incidence of Grade 2 or higher diarrhoea from 20% to 12% ranges from 82% to 36%, if the assumed incidence in the control group is 32%, using a one-sided test with an alpha level of 0.025 ([Table 3-2](#)) [Table 3-2](#).

Table 3-2 Sensitivity of sample size based on 32% control incidence of Grade 2 or more diarrhoea

Incidence, no prophylactic octreotide	32%	32%	32%	32%	32%
Incidence, prophylactic octreotide	12%	14%	16%	18%	20%
Estimated Statistical Power	82%	72%	60%	48%	36%
Subjects per Treatment group	70	70	70	70	70

Power calculations were performed using nQuery software version 7.0.

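### The stated power uses raw diarrhoea rates with no withdrawal, but the primary ITT test scores early withdrawals as Grade 2+ events, so the power tables do not describe that test unless early withdrawal is negligible or sufficiently lower on octreotide

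*Protocol*

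**What the plan says.** **Power.** Protocol 9.2.1 plans "a total of 140 subjects will be randomised in a 1:1 ratio i.e. 70 subjects in each treatment arm". Section 9.2.2 then says "an incidence of 20% of Grade 2 or higher diarrhoea is assumed" for the control arm, citing EGF111438, and reports power that "ranges from 69% to 25%, if the assumed incidence in the control arm is 20" percent (Table 21). A second set, with a 32% control rate attributed to EGF100151, runs from 82% to 36% (Table 22). Both use a one-sided 0.025 level. SAP 3.2 carries the same figures over: power "ranges from 69% to 25%, if the assumed incidence in the control group is 20" percent (Tables 3-1 and 3-2). Neither sample-size section mentions withdrawal.

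**Primary analysis.** Protocol 9.3.5 sets the missing-data rule for the ITT analysis: "Subjects who withdraw from the study prior to the Week 9 visit without experiencing Grade 2 diarrhoea or above will be assumed" to have had such an event. SAP 2.5.2.1 has the same rule with a slightly different cut-off: "Subjects who withdraw from the study on or prior to the Cycle 4 visit date will be assumed to have experienced diarrhoea" of Grade 2 or higher. SAP 2.5.3 applies it to the ITT and m-ITT analyses and drops it for the per-protocol analysis.

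**Interim.** Protocol 9.3.4.2 illustrates conditional power with observed rates. With 30% on control, for about 50% conditional power, "we would need to see a diarrhoea rate of 16% or lower in the octreotide arm".

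**The concern.** The power tables and the primary test use different endpoints. The tables compare the chance of Grade 2+ diarrhoea in each arm. The test compares the chance of Grade 2+ diarrhoea or early withdrawal. If withdrawal is unrelated to treatment, imputation raises both rates, shrinks the difference between them and usually increases its variance, so power falls. If withdrawal differs between arms, the difference enters the p-value as though it were a diarrhoea effect. Imbalance is possible here: the trial is open label, and only the octreotide arm waits 7 days before cancer treatment starts. At stake are what the documents say the design could detect and, for the final report, whether the primary result reflects diarrhoea or withdrawal.

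**Working it through.** **Inputs from the documents.** n = 70 per arm; one-sided alpha 0.025 (z = 1.96); control rates 20% and 32%; octreotide rates 6, 7, 8, 10, 12% and 12, 14, 16, 18, 20%. The 20% is a raw adverse-event rate: Protocol Table 4 gives 38 + 16 = 54 subjects with maximum Grade 2 or higher among 269 treated, which is 20.1%.

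**Assumed input.** d is the proportion withdrawing early, taken as independent of diarrhoea. Neither document gives it. The range used is 5% to 20%.

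**Formula.** Power = Φ[(pc − pt − 1.96·SE0) / SE1], where SE0 = √(2·p̄(1 − p̄)/70), p̄ is the mean of the two rates, and SE1 = √([pc(1 − pc) + pt(1 − pt)]/70).

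**Reproducing the stated power (d = 0).** For 20% v 6%: SE0 = 0.0568 and SE1 = 0.0556, so power = Φ[(0.14 − 0.1113)/0.0556] = 69.6%. All ten entries come out within 2 percentage points of the stated values, so the tables are right for raw rates and zero withdrawal.

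**With the planned imputation.** A subject without an event who withdraws becomes an event, so p becomes p + d(1 − p). For 20% v 6% at d = 10%: control 0.20 + 0.10 × 0.80 = 0.280; octreotide 0.06 + 0.10 × 0.94 = 0.154. The difference falls from 0.14 to 0.126, which is (1 − d) times the raw difference. SE0 = 0.0697, SE1 = 0.0689, and power = Φ[(0.126 − 0.1366)/0.0689] = 44%.

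Power (%) with equal withdrawal in both arms:

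| d | 20% control v 6 / 7 / 8 / 10 / 12% | 32% control v 12 / 14 / 16 / 18 / 20% |
|---|---|---|
| Stated | 69 / 61 / 53 / 37 / 25 | 82 / 72 / 60 / 48 / 36 |
| 0 | 69.6 / 61.6 / 53.5 / 38.0 / 25.0 | 82.2 / 72.0 / 60.3 / 48.1 / 36.5 |
| 5% | 54.8 / 47.9 / 41.4 / 29.5 / 19.9 | 73.3 / 62.9 / 51.9 / 41.1 / 31.3 |
| 10% | 43.9 / 38.4 / 33.1 / 23.9 / 16.6 | 64.6 / 54.8 / 44.9 / 35.5 / 27.1 |
| 20% | 30.0 / 26.4 / 23.0 / 17.1 / 12.4 | 49.8 / 41.7 / 34.0 / 27.0 / 20.9 |

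**Where the 20% comes from.** With the 27.1-week median progression-free survival in Protocol Table 1 and an exponential curve, 1 − 2^(−9/27.1) = 20.6% have progressed or died by week 9. This bears on d only if those subjects count as withdrawn.

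**Unequal withdrawal, real effect.** With 10% control v 15% octreotide, power is 19% for 20% v 6% and 41% for 32% v 12%. With 10% control v 5% octreotide it is 74% and 85%, above the stated 69% and 82%.

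**Unequal withdrawal, no effect.** Take 20% true diarrhoea in both arms. With 20% control v 10% octreotide withdrawal, the analysed rates are 0.20 + 0.20 × 0.80 = 0.36 and 0.20 + 0.10 × 0.80 = 0.28. The chance of a one-sided rejection in favour of octreotide is Φ[(0.08 − 1.96 × 0.0788)/0.0786], about 17% against a nominal 2.5%. With the arms reversed it is Φ[(−0.08 − 1.96 × 0.0788)/0.0786], about 0.1%.

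**The case against.** The best defence is that the arithmetic is correct, the tables are labelled as sensitivity, and both documents say the sample size was not chosen to detect a pre-specified reduction. Counting withdrawals as failures is a pre-specified convention. Recruitment has also ended: SAP 1 and 2.9 report that the trial stopped for futility after 62 patients had enrolled, so restating power at 70 per arm cannot change its size or conduct. All of this stands. It makes the power part a matter of accurate documentation, but it does not make the tables describe the planned test.

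Four stronger readings are tempting and not supported.

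- *Power is certainly lower than stated.* Neither document gives a withdrawal rate by arm, and enough of an imbalance in octreotide's favour raises power above the stated values.
- *The conditional-power examples are wrong.* Protocol 9.3.4.2 does not say its rates are raw, describes an analysis of the primary endpoint, and requires recalculation on the actual incidence. If the rates already include imputed cases, no correction applies. If they are raw, conditional power for 30% v 16% would be about 40%, 33% and 22% at d = 5%, 10% and 20%. The gap is that the text does not say which.
- *The rule inflates false positives for octreotide.* The 17% needs more withdrawal on control. The one arm-specific feature noted above, the 7-day wait, falls on octreotide and would push the other way.
- *There is no unimputed ITT analysis.* SAP 2.5.2.2 and 2.5.3 summarise Grade 2+ diarrhoea over the entire treatment period without imputation, and SAP 2.6.1.3 gives Kaplan-Meier estimates for any-grade diarrhoea. What is missing is an unimputed ITT result for Grade 2+ diarrhoea in the 9-week primary window. The m-ITT analysis keeps the imputation. The per-protocol analysis drops it but changes the population, and is not run if that population exceeds 95% or is below 50% of ITT.

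It would also go too far to say that the rule discards fully observed outcomes. Protocol 7.4.7 collects adverse events for 30 days after discontinuation, so a subject leaving at week 2 is observed only to about week 6, and SAP 2.7.4 keeps nothing after consent is withdrawn.

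**Conclusion.** The mismatch is real. The stated 69-25% and 82-36% are the power of a comparison of raw rates with no withdrawal, and the primary test is a different comparison. They carry over only if early withdrawal is negligible or sufficiently lower on octreotide. With equal withdrawal, power has already dropped by more than 2 points at a rate of about 1-2%, and at 5% the leading figures fall from 69% to 55% and from 82% to 73%.

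These sizes rest on an assumed d that is independent of diarrhoea. The 20% row further requires that progression count as withdrawal. Protocol 4.3.3 classes progression or death during treatment as completing the study, while 4.3.2 lists progression among the reasons for permanent discontinuation and requires a subject who has permanently discontinued to be withdrawn. Until these sections are reconciled, who is imputed is not fixed.

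For the final report, the more useful half of the point is that the p-value cannot separate diarrhoea from withdrawal, and no planned analysis does so in the same population and window.

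**What to change.** 1. Restate Protocol Tables 21 and 22 and SAP Tables 3-1 and 3-2 for the imputed endpoint, p + d(1 − p), over a stated range of d that includes unequal values. Alternatively, state beside the tables that they assume no early withdrawal.
2. Reconcile Protocol 4.3.2 with 4.3.3 for the purpose of the imputation, so that it is clear who is scored as an event, and say whether the interim rates in 9.3.4.2 include imputed cases.
3. In the primary results table, split each arm's count into observed Grade 2+ events and imputed withdrawals, the latter by reason. Add one ITT sensitivity analysis of Grade 2+ diarrhoea in the 9-week window without imputation, using adverse events collected up to 30 days after discontinuation; a cumulative-incidence risk difference at day 63 would do.

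The cost is a recalculation, one extra table and, under equal withdrawal, a lower stated power. No new data are needed.

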**Table 21 Sensitivity of sample size based on 20% control incidence of Grade 2 or more diarrhoea**

Incidence, placebo	20%	20%	20%	20%	20%
Incidence, prophylactic octreotide	6%	7%	8%	10%	12%
Power	69%	61%	53%	37%	25%
Subjects per Treatment Arm	70	70	70	70	70

Based on the results of EGF100151, an incidence of 32% of Grade 2 or higher diarrhoea is assumed for subjects who receive lapatinib and capecitabine with no prophylactic octreotide. The power for the analysis to detect a reduction in the incidence of Grade 2 or higher diarrhoea from 20% to 12% ranges from 82% to 36%, if the assumed incidence in the control arm is 32%, using a one-sided test with an alpha level of 0.025 (Table 22).

**Table 22 Sensitivity of sample size based on 32% control incidence of Grade 2 or more diarrhoea**

Incidence, placebo	32%	32%	32%	32%	32%
Incidence, prophylactic octreotide	12%	14%	16%	18%	20%
Power	82%	72%	60%	48%	36%
Subjects per Treatment Arm	70	70	70	70	70

Power calculations were performed using nQuery software version 7.0.

### 9.2.3. Sample Size Re-estimation

Sample size re-estimation is not planned for this study.

## 9.3. Data Analysis Considerations

### 9.3.1. Analysis Populations

The Intent-to-Treat (ITT) population will comprise all randomised subjects regardless of whether or not treatment was administered. This population will be based on the treatment to which the subject was randomised. Any subject who receives a treatment randomisation number will be considered to have been randomised. The primary analysis of disease efficacy and all diarrhoea-related efficacy endpoints will be conducted using the ITT population.

The modified ITT (m-ITT) population will comprise all subjects in the ITT population who do not show intolerance to octreotide in the s.c. formulation and who do not have diarrhoea recorded as an AE after the first dose of octreotide LAR and prior to the start of treatment with lapatinib and capecitabine. The supplementary analysis of all diarrhoea-related efficacy endpoints will be conducted using the m-ITT population.

The Per-Protocol (PP) population will comprise all randomised subjects who receive at least one dose of study treatment and who comply closely with the protocol. Major protocol violations that would exclude subjects from the PP population will be defined and documented in the Reporting and Analysis Plan (RAP) prior to database release. The PP population will not be analysed if this population comprises more than 95% of the ITT population.

The Safety population will comprise all randomised subjects who receive at least one dose of study treatment and will be based on the actual treatment received if this differs from that to which the subject was randomised. This population will be used for the analysis of clinical safety data.

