The eCRF, the DMD and the FACIT-D are considered to be independent source data, and the investigator must not use the DMD and FACIT-D to supplement information recorded in the eCRF. This study provides an opportunity to compare and contrast investigator-reported outcomes and PROs for each treatment group within the setting of a single controlled clinical study, although differences between the eCRF data and the PRO data will preclude formal comparisons.

Diarrhoea is an AE associated with octreotide treatment in more than 10% of patients [Octreotide SPC]. Octreotide-associated diarrhoea usually occurs following the first dose of octreotide, and is usually mild in severity lasting only a few days [McKeage, 2003]. Diarrhoea associated with octreotide treatment could potentially confound the subsequent assessment of diarrhoea associated with treatment with lapatinib and capecitabine. The primary analysis of efficacy will be based on the total ITT population (Section 9.3.1). Supplementary analyses of efficacy will be based on a modified intent-to-treat (m-ITT) population, which will exclude subjects with diarrhoea reported following the first dose of octreotide LAR and prior to the first dose of lapatinib and capecitabine and will also exclude subjects with intolerance to the octreotide 0.1mg s.c. dose (Section 9.3.1).

The efficacy of prophylactic octreotide in the prevention of diarrhoea associated with treatment with lapatinib and capecitabine or in the management of diarrhoea associated with treatment of MBC is not known and is being explored for the first time in LAP117314. It is possible that prophylactic treatment with octreotide may provide no benefit for subjects, and could potentially worsen the frequency and severity of diarrhoea in this study. However, it is difficult to predict what the incidence or severity of octreotide-associated diarrhoea (and other AEs) might be in LAP117314, where subjects will receive only two doses of octreotide LAR, where the time taken to achieve clinically relevant circulating concentrations of octreotide is unknown, and where exposure to octreotide at clinically relevant doses is expected to last for no more than 12 weeks. A GSK Safety Review Team (SRT) will be established to review safety data in this study on an ongoing basis, in order to protect subjects' interests and to ensure their safety.

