### **3. INVESTIGATIONAL PLAN**

#### **3.1. Study Design**

This is a randomised, parallel group, multi-centre, open-label Phase II study in subjects with HER2-positive metastatic breast cancer which has progressed following prior therapy, which must have included anthracyclines and taxanes and therapy with trastuzumab in the metastatic setting. This study is not placebo controlled, and there is no active comparator.

Protocol waivers or exemptions are not allowed with the exception of immediate safety concerns. Therefore, adherence to the study design requirements, including those specified in the Time and Events Schedule ([Table 16](#), and [Table 17](#)), is essential and required for study conduct.

Supplementary study conduct information not mandated to be present in this protocol is provided in the accompanying SPM. The SPM will provide the site personnel with administrative and detailed technical information that does not impact subject safety.

Subjects must be screened for eligibility and informed consent must be given before any study-related procedures are conducted.

All subjects will receive treatment with lapatinib 1250mg once daily and capecitabine 1000mg/m^2 twice daily until disease progression. Lapatinib will be given every day; capecitabine will be given in 3 week cycles of two weeks treatment followed by one week off treatment.

Subjects will be randomised in a 1:1 ratio to receive either:

- Octreotide (Sandostatin LAR) 40mg 7 days before the start of treatment with lapatinib and capecitabine and again 28 days later, or
- No octreotide treatment.

For subjects randomised to receive octreotide, treatment with lapatinib and capecitabine will be initiated 7 days after the first dose of octreotide given as the LAR formulation. For subjects randomised to receive no octreotide, treatment with lapatinib and capecitabine will be initiated immediately following enrolment.

Subjects randomised to receive octreotide LAR must be given one 0.1mg dose of the standard formulation of octreotide s.c. to assess tolerability at least one hour before the first dose of the LAR formulation is administered. Subjects with significant intolerance to octreotide 0.1mg s.c. will not receive treatment with octreotide LAR, but will receive treatment with lapatinib and capecitabine as scheduled.

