2.1.3.2 Reference start date

There are three reference start dates:

- Age is an eligibility requirement and therefore the reference start date for age is the date of screening.
- The safety reference start date is the date of a subject receiving the first dose of study treatment (i.e., octreotide, lapatinib or capecitabine).
- The efficacy reference start date is the date of randomization and will be used to calculate study day for efficacy measures and baseline characteristics.

The reference start date for all other, non-safety assessments (i.e., tumor assessment, death, disease progression, tumor response, ECOG performance status, and patient reported outcomes (PRO)) is the date of randomization.

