2.2 Analysis Populations

Intent-to-Treat Population

The Intent-to-Treat (ITT) population will comprise all randomised subjects regardless of whether or not treatment was administered. This population will be based on the treatment to which the subject was randomised. Any subject who receives a treatment randomization number will be considered to have been randomised. The primary analysis of disease efficacy and all diarrhoea-related efficacy endpoints will be analysed using the ITT population.

Modified ITT

The modified ITT (m-ITT) population will comprise all subjects in the ITT population and under Octreotide arm this population will include subjects who do not show intolerance to octreotide in the s.c. formulation and who do not have non treatment related diarrhoea recorded

as an AE after the first dose of octreotide LAR and prior to the start of treatment with lapatinib and capecitabine. A sensitivity analysis of diarrhoea-related primary efficacy endpoint will be conducted using the m-ITT population.

Per Protocol Population

The Per-Protocol (PP) population will comprise all randomised subjects who receive at least one dose of study treatment and who comply closely with the protocol (that is subjects who are not excluded from PP set as per PDMP). The PP population will not be analysed if this population comprises more than 95% or less than 50% of the ITT population. The analysis of primary efficacy endpoint will be repeated using the PP population.

Subjects with potential PDs will be excluded from PP population based on Protocol Deviation Management Plan (PDMP).

Safety Population

The Safety population will comprise all randomised subjects who receive at least one dose of study treatment and will be based on the actual treatment received if this differs from that to which the subject was randomised. This population will be used for the analysis of clinical safety data. Moreover, if a subject who was randomised to Octreotide arm, showed intolerance to octreotide in the s.c. formulation, and took at least one dose of lapatinib or capecitabine, then subject will be included in no Octreotide arm for safety analysis.

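### The m-ITT summary of the primary endpoint drops subjects from the octreotide arm only, so it does not compare randomised groups

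*Protocol*

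**What the plan says.** Protocol 1.2 and 9.3.1 make ITT the primary population and add m-ITT as a supplementary one. Section 1.2 explains that diarrhoea caused by octreotide could confound the later assessment. It therefore describes the supplementary set as one "which will exclude subjects with diarrhoea reported following the first dose of octreotide LAR and prior to the first dose of lapatinib and capecitabine"; those intolerant of the s.c. test dose are removed too. Section 9.3.1 words the diarrhoea criterion as keeping subjects "who do not have diarrhoea recorded as an AE after the first dose of octreotide LAR and prior to the start of treatment".

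The arms differ before anticancer treatment begins. In the octreotide arm, "treatment with lapatinib and capecitabine will be initiated 7 days after the first dose of octreotide given as the LAR formulation" (Protocol 3.1). The same section says: "For subjects randomised to receive no octreotide, treatment with lapatinib and capecitabine will be initiated immediately following enrolment".

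SAP 2.2 places the restriction in one arm explicitly: "under Octreotide arm this population will include subjects who do not show intolerance to octreotide in the s.c. formulation". It also narrows the diarrhoea criterion to episodes not related to treatment, a limit the protocol does not have. SAP 4, which records changes from the protocol, does not mention this.

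The endpoint window also differs between the documents. Protocol 9.3.5.1.1 counts Grade 2+ episodes in the first 9 weeks of lapatinib and capecitabine. In SAP 2.5.2.1 the episodes that count "are defined as those with an onset date on or after the efficacy reference start date", up to the Cycle 4 visit, and SAP 2.1.3.2 adds: "The efficacy reference start date is the date of randomization".

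SAP 2.5.4 summarises the primary endpoint in m-ITT without a statistical test.

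**The concern.** A sensitivity analysis should test the primary result while keeping the comparison that randomisation protects. Here subjects leave one arm because of events after allocation, and their counterparts in the control arm cannot be identified and stay in. If subjects with early diarrhoea or early intolerance are also more likely to have Grade 2+ diarrhoea later, the octreotide arm is left with a lower-risk remainder.

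The SAP supports a clinical study report and a publication, and SAP 2.2 calls m-ITT a sensitivity analysis of the primary endpoint. The per-protocol summary is dropped if that population exceeds 95% or falls below 50% of ITT, so m-ITT may be the only alternative-population result printed beside ITT. Even an untested table could then be read as support for octreotide that it cannot give.

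**Working it through.** **1. Can a control subject be excluded?** The criteria are intolerance to s.c. octreotide, and diarrhoea between the first LAR dose and the start of lapatinib and capecitabine. Controls receive neither the test dose nor LAR and have no run-in. The answer is no under both documents.

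**2. Does the exclusion overlap the endpoint?** Under Protocol 9.3.5.1.1 it does not, because the run-in ends before counting starts. Under SAP 2.5.2.1 it does: a Grade 2+ run-in episode is an event in ITT, and m-ITT deletes it with the subject if she meets the exclusion. A second route is imputation. A withdrawal on or before the Cycle 4 visit counts as Grade 2+ (SAP 2.5.3). An s.c.-intolerant subject who withdraws early is thus a failure in ITT and absent from m-ITT, while an early-withdrawing control remains a failure.

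**3. The plan's own figures.** Neither document sizes this effect. The control rates used here, 20% and 32%, are those of Protocol 9.2.2 (70 per arm, one-sided 0.025). The pooled-variance normal approximation reproduces those power tables: 69.6, 61.6, 53.5, 38.0 and 25.0% against the stated 69, 61, 53, 37 and 25%; and 82.2, 72.0, 60.3, 48.1 and 36.5% against 82, 72, 60, 48 and 36%.

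**4. Shift with no true octreotide effect.** Let p be the true rate in both arms, f the share of the octreotide arm excluded, and R the risk of those excluded relative to the others. The rate in those who remain is p / (fR + 1 − f). Both f and R are assumptions. The only anchor is Protocol 1.2: "Diarrhoea is an AE associated with octreotide treatment in more than 10% of patients". That is not a 7-day figure.

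| f | R | m-ITT rate, p = 20% | Shift (points) | m-ITT rate, p = 32% | Shift (points) |
|---|---|---|---|---|---|
| 5% | 2 | 0.20/1.05 = 19.0% | 1.0 | 0.32/1.05 = 30.5% | 1.5 |
| 10% | 2 | 0.20/1.10 = 18.2% | 1.8 | 0.32/1.10 = 29.1% | 2.9 |
| 15% | 2.5 | 0.20/1.225 = 16.3% | 3.7 | 0.32/1.225 = 26.1% | 5.9 |

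With R = 1 the shift is zero.

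**5. Direction and extremes.** Now let q be the absolute risk of those excluded, so the m-ITT rate is (p − fq)/(1 − f). Take f = 10% throughout.
- At half the average risk the shift reverses: (0.20 − 0.01)/0.90 = 21.1% and (0.32 − 0.016)/0.90 = 33.8%, which is 1.1 and 1.8 points against octreotide.
- If every excluded subject were already a counted event under the SAP (q = 1), the rates would be 0.10/0.90 = 11.1% and 0.22/0.90 = 24.4%, shifts of 8.9 and 7.6 points. This is an extreme case, since Protocol 1.2 describes octreotide-associated diarrhoea as usually mild.

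**6. At the size reached.** SAP 1 reports 62 enrolled at the interim. Assuming 31 per arm, 5-15% is 1.6 to 4.7 subjects. If three excluded subjects all had events, 6/31 (19.4%) would become 3/28 (10.7%).

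**The case against.** The case on the other side is substantial. ITT is primary throughout, m-ITT is supplementary in the protocol, and SAP 2.5.4 makes it descriptive. The SAP was written after the trial had been stopped for futility, so at stake are a few subjects in an untested table of an abbreviated report. There are other ITT views as well, such as the entire-period summary without imputation (SAP 2.5.2.2 and 2.5.3). All of this stands and limits the weight of the point.

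The assumed share may also be too high. Protocol 3.2 notes that octreotide levels may be too low to cause adverse events in the first 7 days, and entry requires 14 days free of diarrhoea. The SAP's limit to unrelated diarrhoea shrinks the share further: study treatment includes octreotide (SAP 2.1.3.1) and missing relatedness is set to yes (SAP 5.1), so octreotide-related run-in diarrhoea stays in m-ITT. That is fair, but it brings its own problem. Read literally, the SAP keeps the cases Protocol 1.2 wanted to remove and removes background cases of a kind that controls can also have.

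One could also argue that m-ITT offsets the roughly 7 extra days at risk that the SAP window gives the octreotide arm. The extra days are real and work against octreotide. Removing whole subjects from one arm is not a valid correction, because it also discards their follow-up on lapatinib and capecitabine.

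A reader might infer that the exclusion is made on the outcome itself, or that it necessarily builds in a benefit. The documents support neither. Under the protocol window the run-in precedes the endpoint, and the overlap in the SAP is confined to Grade 2+ episodes that meet its exclusion. The direction depends on the risk of those removed, on which the documents give no data. It is least certain for s.c. intolerance, since those subjects receive no LAR.

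**Conclusion.** The point holds in a limited form. It is certain from the text that m-ITT excludes subjects for post-randomisation events possible in only one arm, so it does not compare randomised groups. A tilt towards octreotide is likely but not certain: it requires that excluded subjects are at above-average risk, or that they carry events or imputed failures which the SAP already counts. Under the assumptions in the table (5-15% excluded, at 2-2.5 times the risk of the others) the shift is about 1-4 points at a 20% rate and 1.5-6 points at 32%. The true size is unknown. The primary conclusion is not affected. The risk is that a supportive table is over-read, and that the SAP and protocol exclude different subjects under the same population name.

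**What to change.** In SAP 2.2 and 2.5.4, replace the m-ITT summary with one that keeps all randomised subjects. Count Grade 2+ episodes with onset from the first lapatinib and capecitabine dose to the Cycle 4 visit in both arms, and retain the existing non-responder imputation, which also covers subjects who withdraw before starting lapatinib and capecitabine. This is the window of Protocol 9.3.5.1.1. Under the protocol alone it would duplicate the primary analysis; it adds information here because the SAP starts its ITT window at randomisation. Flag run-in episodes in the by-subject diarrhoea listing already planned in SAP 2.6.1.2.

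If m-ITT is kept, label it as a non-randomised comparison and report the number excluded and the reasons. Reconcile the SAP's relatedness limit with Protocol 1.2 and 9.3.1, and record the outcome in SAP 4.

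The cost is SAP wording and one table rerun with a different start date. No new data are needed, and SAP 2.6.1.3 already uses the first lapatinib and capecitabine dose as its time origin.
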